Common clinical biomarkers related to FD nephropathy (alpha-1-microglobulin, microalbumin, creatinine) will be compared with the pivotal biomarkers associated with the inflammatory and dysregulated immune pathways.

Table 2: Suggested pivotal biomarkers and pathways involved in Fabry nephropathy:

	Relationship to pathway or involvement	Biomarkers	
Inflammatory biomarkers	Cytokines	NF- κ B pathway	IL-1 β , IL-6, TNF- α , IL-10
		TGF- β 1 pathway	TGF- β 1, IL-4, INF-gamma
		TLR4 pathway	IL-18, IL-12
	Chemokines	NF- κ B pathway	MCP1, IL-8, RANTES, BAFF , APRIL
		TLR4 pathway	PAI-1
Biomarkers of kidney function and proteinuria	clinical laboratory urine biomarkers	alpha-1-microglobulin, albumin, cystatin C, GFR	
	We will measure in our laboratory	B2M, bikunin, NGAL, osteopontin, clusterin, creatinin.	
Acute kidney injury	Marker of renal tubular injury	KIM-1	
	Inflammation-associated glycoprotein	YKL-40	
	Growth factor, fibrosis	EGF	
	Apoptotic marker	CK-18 M30	
	Pyroptotic markers	IL-1β, IL-18 (included in the list of cytokines)	

This is a study to assess the markers related to autophagy, apoptosis, pyroptosis, and inflammatory markers related to NFkB, TNF-alpha, and TGF-β1 pathways in the urine. Urinary biomarkers will then be compared to the standard measures of kidney function and proteinuria: GFR, cystatin-C, B2M, bikunin, NGAL. Gb3 and Lyso-Gb3, urine microalbumin, and urine protein-to-creatinine (UPCR) ratio. We will also analyze the role of therapy, especially for the inflammatory responses in patients on stable enzyme replacement therapy (ERT) with that of patients naïve to therapy.

OBJECTIVE AND SPECIFIC AIMS

Primary objective: Identify biomarkers in urine for the detection and progression of kidney involvement in naïve male and female patients with FD, and compare with patients on ERT to assess the effects of ERT.

Specific Aims:

- 1) *To identify urinary inflammatory biomarkers associated with nephropathy in FD.*
- 2) *Analyze the association between urinary inflammatory markers, clinical urine biomarkers, circulating lyso-Gb3, and kidney involvement in naïve FD patients.*
- 3) *Analyze the association between urinary inflammatory markers, clinical urine biomarkers, circulating lyso-Gb3, and kidney involvement in FD patients on stable ERT.*

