- 4) *Assess the role of the time of initiation and duration of therapy (ERT), respectively, inactivation and reversibility of inflammation cascade, and how these relate to the degree of kidney involvement in patients with FD.*

SUBJECT SELECTION

Number of Subjects

A total of 50 subjects, male or female, between the ages of 18 to 80 years of age, include 25 healthy individuals and 25 patients with Fabry disease.

Study population

FD patients n=25 (5 without clinical evidence of nephropathy and 15 patients with clinical evidence of nephropathy), NAÏVE FD patients (n=5), and healthy controls n=25 (controls, urine samples are not actual patients, urine samples will be purchased from a commercial company).

The study will involve 50 age-and gender-matched subjects and controls divided into the following cohorts:

1. FD subjects without clinical evidence of nephropathy (normal eGFR and no microalbuminuria) naïve or on ERT (**n=5**),
2. FD subjects with clinical evidence of nephropathy (**n=15**)
 Subcohorts:
 - a. FD subjects on ERT with CKD stage 1 (estimation n=5)
 - b. FD subjects on ERT with CKD stage 2 (estimation n=5)
 - c. FD subjects on ERT with CKD type 3 a or b (estimation n=5)
3. FD patients naïve to therapy (**n=5**). Can we be included in Cohort group 1 or 2.
 Additional analysis will be stratified NAÏVE vs. ERT.
4. Non-FD age-matched controls with no known kidney disease n=25.

	FD	Healthy control
Total FD	25	25
without nephropathy	5	
with nephropathy	15	
NAÏVE	5	

Table 3. Clinical staging of FD patients:

Clinical parameter(s)	FD patients and kidney involvement				Age-matched controls
	Stage 1	Stage 2	Stage 3a	Stage 3b	
Kidney involvement					
Kidney damage	Normal/	Mild reduction	Moderate reduction	Moderate reduction	normal
GFR ml/m1.73 m ²	>90	60-89	45-59	30-44	90 min
Cystatin-C	0.5-0.9	1.0-1.2	1.3-1.5	1.4-1.9	0.5-0.9
Urine B2M	-	0.428-0.603	0.603-0.950	0.950-1.034	-
FD biochemical markers					
α-Gal A	Deficiency	Deficiency	Deficiency	Deficiency	Normal
GLA mutations	Yes	yes	yes	yes	No
Gb-3	Yes	yes	yes	yes	No
Lyso-Gb-3	Yes	yes	yes	yes	No

Gender of Subjects

Subjects of both genders will be included in the research, and it is expected that this inclusion will be representative of the FD patients population.

Age of Subjects

Subjects will be between the age of 18 to 80 years of age.

Racial and Ethnic origin

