This prospective study aims to establish novel biomarkers for non-invasive detection of kidney involvement in FD. FD patients will be assessed using the definition of Kidney Disease Outcomes Quality Initiative (KDOQI) 2002. The patients with CKD stages 3 or less with a progressive decline in kidney function, as evidenced by a decreasing GFR and a slope of less than -1.5, will be further assessed.

The glomerular filtration rate will be calculated from serum creatinine (CKD-EPI). The UPCR will be used to measure proteinuria. Additionally, the patients will be stratified as having low renal involvement (LRI) if the UPCR is less than or equal to 0.5 g/g. Anti-drug antibody status and other adverse events, such as the occurrence and the progression of cardiomyopathy as evidenced by LVMI, LVPWD, and neurological events such as strokes, will be recorded through the study. The categorization of kidney involvement via renal biomarkers will be defined (Table 4).

Table 4. Clinical staging of FD patients:

Clinical parameter(s)	FD patients and kidney involvement				Age-matched controls
	Stage 1	Stage 2	Stage 3a	Stage 3b	
Kidney involvement					
Kidney damage	Normal/	Mild reduction	Moderate reduction	Moderate reduction	Normal
GFR ml/min/1.73 m ²	>90	60-89	45-59	30-44	90 min
Cystatin-C	0.5-0.9	1.0-1.2	1.3-1.5	1.4-1.9	0.5-0.9
Urine B2M	-	0.428-0.603	0.603-0.950	0.950-1.034	-
FD biochemical markers					
α-Gal A	Deficiency	Deficiency	Deficiency	Deficiency	Normal
GLA mutations	Yes	yes	yes	yes	No
Gb-3	Yes	yes	yes	yes	No
Lyso-Gb-3	Yes	yes	yes	yes	No

The study will take place over 24 months. The clinical part of the active study to collect clinical data and the samples will be over 12 months. The urine samples will be collected three times (0, 6, and 12 months) (Table 5). A physical examination will be performed during the visits, and samples will be collected. We will review medical records as a part of the clinical evaluation. After a urine specimen collection, samples will be aliquoted and stored at -80⁰ C until biomarkers are screened. We expect to recruit the subjects within 6 months of the study initiation; thus, the last visit for the last subject is expected to be 19 months after the study starts.

Table 5. Visit and assessment schedule:

visits	baseline		
	1	2	3
	month 1/ enrollment	month 6	month 12
Vital signs	X	X	X
Height and weight	X		X
Physical examination	X		X
Concomitant medications	X	X	X
Adverse event reporting	X	X	X
Informed consent form	X		

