Events/issues which are part of the study objectives or endpoints will be systematically identified and collected from healthcare records or other applicable source records and summarized as part of any interim analysis and in the final study report. Such events do not need to be notified as individual reports to Takeda Pharmacovigilance.

Events/Issues which are not part of the study objectives and endpoints will not be abstracted or collected from healthcare records or other applicable source records.

Reporting of Adverse Drug Reactions to Regulatory Agencies and IRB/EC

LDRTC is responsible for reporting serious and non-serious adverse drug reactions suspected of being related to regulatory authorities. The Investigator is responsible for reporting adverse drug reactions to the IRB/EC, if required by national law or regulation, within the timelines required by such law or regulation. The Investigator shall maintain records of all such submissions.

Study-specific committees

No steering committee, data safety monitoring committee, or clinical endpoint committee will be used in this study.

STUDY OVERSIGHT

Premature Termination of Study:

[name], may prematurely terminate the study. Reasons for termination may include but is not limited to the following:

- Series of adverse events or incidences associated with subject participation.
- Low subject enrollment.

Clinical Research Quality Assurance:

To ensure that GCP and good clinical research are conducted per regulatory requirements and guidelines, the study will be made available for monitoring, auditing, review, and inspection by regulatory authorities such as IRB and FDA. This will be accomplished by providing direct access to study-related documents.

Data management

The acquired data will be entered into Excel for further analysis. Data will be analyzed using GraphPad Prism software (Graphpad Inc., La Jolla, CA) using ANOVA analysis and Student's t-test for statistical analysis. $p < 0.05$ is considered significant.

Samples and data storage

Once subjects have signed the informed consent form, they will be assigned a personal generic research study identification number. This number will be matched with the patient's name and demographic information in a file stored on a password-protected computer. Only members of the research team at **Lysosomal & Rare Disorders Research & Treatment Center, Inc** will have

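### Albumin and GFR, and cystatin-C and urine B2M if Table 4 sets the categories, both define kidney involvement and are analysed against it, so their p-values are uninterpretable and they are not a fair benchmark on that label

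*Protocol*

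**What the plan says.** - Objective and Specific Aims: Aim 2 is "Analyze the association between urinary inflammatory markers, clinical urine biomarkers, circulating lyso-Gb3, and kidney involvement in naïve FD patients". Aim 3 covers the association of "clinical urine biomarkers, circulating lyso-Gb3, and kidney involvement in FD patients on stable ERT".
- Table 2: the clinical laboratory urine biomarkers are "alpha-1-microglobulin, albumin, cystatin C, GFR". A separate row, for assays in the study's own laboratory, lists "B2M, bikunin, NGAL, osteopontin, clusterin, creatinin".
- Brief Rationale and Background: the common clinical markers ("alpha-1-microglobulin, microalbumin, creatinine) will be compared with the pivotal biomarkers associated with the inflammatory and dysregulated immune pathways"). The paragraph after Table 2 extends the comparators to GFR, cystatin-C, B2M, bikunin, NGAL, Gb3 and lyso-Gb3, microalbumin and UPCR.
- Study population, cohort 1 (n=5): "FD subjects without clinical evidence of nephropathy (normal eGFR and no microalbuminuria) naïve or on ERT". Cohort 2 (n=15) has clinical evidence of nephropathy, with about 5 patients on ERT in each of CKD stage 1, stage 2 and stage 3a/b. The naïve group is n=5.
- Study design and plan: "The categorization of kidney involvement via renal biomarkers will be defined (Table 4"). The graded rows of that table are GFR, cystatin-C and urine B2M. GFR is CKD-EPI from serum creatinine.
- Data management: analysis "using ANOVA analysis and Student's t-test for statistical analysis", with significance at p<0.05.

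**The concern.** If patients are sorted into groups by a measurement and the groups are then compared on it, the comparison has no independent outcome. It asks whether people sorted on X differ in X. The nominal 5% error rate does not apply, and neither a small nor a large p-value says anything about the biology of the kidney.

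Two uses are at stake. First, Aims 2 and 3 could report albumin, GFR or cystatin C as associated with kidney involvement, as though this were a finding on a par with an association for an inflammatory marker. Second, the inflammatory markers are to be compared with the clinical ones. On a label that albumin and GFR define, those two have a head start that a new marker does not have.

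**Working it through.** The protocol gives no power or sample-size calculation, so there is no figure of its own to reproduce. The check has two parts: which measures play both roles, and how large the built-in effect is under the protocol's own tests.

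**Which measures play both roles**

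| Measure | Defines kidney involvement? | Analysed or used as comparator? |
|---|---|---|
| Albumin | Yes (cohort 1) | Yes (Table 2; Aims 2 and 3; comparator) |
| GFR | Yes (cohort 1; Table 4) | Yes (Table 2; Aims 2 and 3; comparator) |
| Cystatin-C | Only if Table 4 categorises | Yes (Table 2; Aims 2 and 3; comparator) |
| Urine B2M | Only if Table 4 categorises | Comparator; not in Table 2's clinical laboratory row |
| Alpha-1-microglobulin, NGAL, bikunin, clusterin, osteopontin | No | Yes, not circular |
| Lyso-Gb3 | No (Table 4 shows it present at every stage) | Yes, not circular |

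**GFR across the three ERT stages, n = 5/5/5**

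Assume values uniform within the Table 4 bands, with stage 1 taken as 90-120 and stage 3 as 30-59.

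- Midpoints: 105, 74.5 and 44.5; grand mean 224/3 = 74.67.
- Between-group mean square: 5 × (30.33² + 0.17² + 30.17²)/2 ≈ 5 × 1830/2 ≈ 4575.
- Within-group variance (width²/12): 75.0, 70.1 and 70.1; mean 71.7.
- F ≈ 4575/71.7 ≈ 64, against a 5% critical value of 3.89 on 2 and 12 degrees of freedom.

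Simulation agrees: p<0.05 in 100% of runs. Cystatin-C in its Table 4 bands also gives 100%. Urine B2M, stage 2 v stage 3 at 5 v 5, gives 99.9%. Pure noise sorted on itself into 5/5/5 gives 100%, so the result carries no biological information.

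**Cohort 1 v cohort 2, n = 5 v 15**

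GFR reaches p<0.05 in 80% of runs and cystatin-C in 76%.

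For albumin, take a marker whose only link to nephropathy is being the grouping criterion. Its log value is normal and is cut at its median. The 5 patients in cohort 1 lie below the cut, k of the 15 lie above it, and the rest are unselected. The test is a two-sided Student's t-test on the same sample that was used for grouping. The floor is k = 5: the planned stage 1 patients have GFR above 90, so by the cohort 1 definition they can be in cohort 2 only through albuminuria.

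| Scale analysed | k = 15 | k = 10 | k = 5 |
|---|---|---|---|
| Log | 100% | 91% | 60% |
| Raw, log SD 1 (assumed) | 73% | 52% | 24% |
| Raw, log SD 2 (assumed) | 15% | 8% | 3% |

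With a separate sample correlating 0.9 with the grouping value, the log row becomes 98%, 76% and 48%. The low raw-scale figures show a t-test failing on skewed data, not an absence of circularity. If all 15 qualify on albuminuria, separation is complete and the exact two-sided rank p is 2/C(20,5) = 2/15,504 = 0.00013.

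**Where the effect is weak or absent**

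- Cohort 1 v stage 1 nephropathy: GFR and cystatin-C have the same ranges in both groups, and p<0.05 occurs in 5-6% of runs, the nominal level.
- Aim 2, about 5 naïve patients: GFR 29-74%, depending on the split; albumin 1-32% on the raw scale and 15-49% on the log scale; noise sorted on itself 13-26%. With complete separation, the smallest exact rank p is 2/C(5,2) = 0.20 for 2 v 3 and 2/C(5,1) = 0.40 for 1 v 4.

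**Effect on the benchmark (worst case)**

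Assume true severity correlates 0.7 with albumin and 0.85 with a better new marker, and group 5 v 15 on albumin alone. Albumin then has an AUC of 1.00 by definition. The better marker averages 0.78, reaches p<0.05 in about half of runs, and equals albumin in about 1%.

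**The case against.** The strongest reply has four parts.

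- **No stated rule.** The protocol does not say that albumin or GFR will be tested as a candidate across the groups it defines. Data management names only the tests and the threshold, and matching tests to markers is commonly left to an SAP. This stands as a limit on what can be claimed. But the outcome definition, the marker list and the aims are all fixed in the protocol, and together they place the same measures on both sides of one association.
- **Reference measures, not candidates.** The clinical measures are mainly a standard, and relating new markers to a standard is ordinary. This also stands: correlating an inflammatory marker with eGFR is not circular. Circularity enters when both are judged on the nephropathy label.
- **Table 4 may be descriptive.** Staging is said to follow KDOQI 2002, the cystatin-C bands for stages 3a and 3b overlap (1.3-1.5 v 1.4-1.9), and urine B2M is blank for stage 1. Hence the case for cystatin-C and B2M is conditional. Albumin and GFR do not depend on it.
- **Using GFR as the only target would do harm.** It would discard albuminuric nephropathy with normal GFR, the very feature that separates stage 1 patients from cohort 1. This is right, and the fix avoids it.

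A reader might infer that the defining measures will pass p<0.05 by construction, or whatever the biology. The figures do not support that: albumin falls to about 3% on a strongly skewed raw scale, and naïve n=5 is far from assured. A reader might also infer that the whole benchmark is circular, or that the protocol plans an accuracy contest which a better marker must lose. Several comparators define nothing, and the protocol names no ROC, AUC or superiority comparison.

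**Conclusion.** The point holds in this form. Albumin and GFR define kidney involvement and are analysed against it. Cystatin-C and urine B2M share the problem if Table 4 is used to categorise. For these measures the association is built in and its p-value is uninterpretable, in whichever direction it falls. On the nephropathy label they are not a fair yardstick for the inflammatory markers.

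The size varies widely: 100% of runs below 0.05 for GFR across three stages of 5, about 3-100% for albumin at 5 v 15, and far from assured in the naïve group. These rates rest on assumed distributions (uniform within the Table 4 bands; lognormal albumin with log SD 1 or 2) and on the planned group sizes. The circularity itself follows from the text and needs none of these assumptions.

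**What to change.** 1. Define kidney involvement from a fixed set already in the protocol, CKD-EPI eGFR and albuminuria. Keep cystatin-C and urine B2M in Tables 3 and 4 as descriptive rows, not as part of the categorisation.
2. In Aims 2 and 3, state that the defining measures are reported by group descriptively, are not tested against that grouping, and do not count as identified markers.
3. Do not rank inflammatory markers against albumin or GFR on the nephropathy label. Compare them there only with clinical markers that do not define it. Report their relation to eGFR and to albuminuria separately, so that albuminuric nephropathy with normal GFR remains a target.

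The cost is a few sentences in the aims and beside Tables 3 and 4, with no new data. The defining measures lose a p-value that carried no information.

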There are no enrollment restrictions based on race or ethnic origin, and it is expected that racial and ethnic representations in this study will represent the FD population.

INCLUSION/EXCLUSION CRITERIA

Inclusion criteria:

- a. Male and Female subject is greater than 18 but not older than 80 years.
- b. Subject willing to sign the informed consent and/or assent.
- c. Confirmed diagnosis of Fabry disease based on deficient α -Gal A enzymatic activity and molecular analysis demonstrating pathogenic variants in the *GLA* gene.

Exclusion criteria:

- a. Any other known genetic condition associated with CKD,
- b. Evidence of hepatitis B or C infections or other chronic infectious diseases,
- c. Pregnancy or breastfeeding.
- d. Any other chronic condition, as per PI's discretion, that makes the subject ineligible.

Description of criteria for withdrawal from the study

A subject may withdraw from the study at any time. The study is entirely voluntary.

RECRUITMENT:

Upon identifying patients with FD disease by the Principal Investigator, the research coordinator will recruit the study subjects. The research coordinator will recruit healthy controls in the clinic or purchase from a commercial company.

SETTING/LOCATION

Research subjects will be recruited at the **Lysosomal and Rare Disorders Research and Treatment Center, Inc (LDRTC)** located at [name], and/or [name].

Subjects recruited at these facilities will be receiving advice from [name], and be under her clinical care. All experimental/laboratory procedures will be performed by or under the supervision of [name]. All informed consent processes will take place at the indicated research sites.

Laboratory tests will be performed at **Lysosomal & Rare Disorders Research & Treatment Center, Inc**, whereas some assays such as Lyso-Gb3 will be performed outside collaborating laboratories such as Labcorp Diagnostic Laboratories and/or Centogene, Rostock, Germany.

STUDY PROCEDURES

Study type

Descriptive and observational study of molecular components detected in biological specimens of urine.

Study design and plan

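### The protocol gives two different sources for the control urine; if all 25 controls are purchased, a Fabry-versus-control difference cannot be attributed to disease rather than to sample source

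*Protocol*

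**What the plan says.** **Source of controls.** Under SUBJECT SELECTION, Study population, the control group is described as "controls, urine samples are not actual patients, urine samples will be purchased from a commercial company". No alternative is offered there. Under RECRUITMENT the text is: "The research coordinator will recruit healthy controls in the clinic or purchase from a commercial company". Neither section says how many controls come from each source.

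**Numbers and comparability.** Number of Subjects states that the 50 subjects "include 25 healthy individuals and 25 patients with Fabry disease". Study population adds "The study will involve 50 age-and gender-matched subjects and controls divided into the following cohorts", and cohort 4 is "Non-FD age-matched controls with no known kidney disease n=25". Controls are also described as healthy and aged 18 to 80. Tables 3 and 4 have a control column with normal kidney status, a GFR entry of 90, cystatin-C 0.5-0.9, normal α-Gal A, and no GLA mutation, Gb-3 or Lyso-Gb-3.

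**Handling.** Fabry patients are recruited at the study centre (SETTING/LOCATION) and give urine at 0, 6 and 12 months. Study design and plan continues: "After a urine specimen collection, samples will be aliquoted and stored at" -80 °C until the biomarkers are screened. No section sets collection, processing or storage conditions for purchased urine before it is received, or says whether the three-visit schedule applies to it.

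**Purpose and analysis.** Study design and plan states: "This prospective study aims to establish novel biomarkers for non-invasive detection of kidney involvement in FD". Data management specifies analysis "using ANOVA analysis and Student's t-test for statistical analysis", with p<0.05 as the criterion.

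**The concern.** The two sections cannot both be followed as written: one fixes purchase, the other leaves a choice. The choice matters because the only design that satisfies both statements is the one in which every Fabry sample comes from the study centre and every control sample from a vendor.

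In that design, anything that differs systematically between centre urine and vendor urine appears in full as a Fabry-versus-control difference. Examples are the way of collection, the delay before freezing and the storage history. Age and gender matching and the clinical description of controls do not address this, because they concern the donor and not the specimen. A handling shift could be reported as a Fabry marker, or could mask a real one. Half of the 50 subjects are controls, and the Protocol gives them no evident use other than comparison with the patients.

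**Working it through.** **1. The plan's own figure.** Fabry cohorts: 5 + 15 + 5 = 25. With 25 controls the total is 50, as stated. The Protocol gives no power, effect size or SD, so there is no power figure to reproduce.

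**2. What can be estimated.** Write a marker as

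Y = a + b·Fabry + c·Purchased + error.

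If all 25 controls are purchased, Purchased = 1 − Fabry, so

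Y = (a + c) + (b − c)·Fabry + error.

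Only b − c can be estimated. The design matrix with columns intercept, Fabry and Purchased has rank 2 of 3. A source covariate added in a later analysis plan would not change this.

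If m controls come from the clinic, rank is 3. The standard error of the source-adjusted Fabry effect, in SD units, is √(1/25 + 1/m):

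| Clinic controls | Purchased controls | Rank | SE of Fabry effect (SD) |
|---|---|---|---|
| 0 | 25 | 2 | not estimable |
| 5 | 20 | 3 | √(0.04 + 0.20) = 0.49 |
| 12 | 13 | 3 | √(0.04 + 0.0833) = 0.35 |

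For comparison, the unadjusted 25 versus 25 standard error is √(2/25) = 0.28 SD. A mixed source makes the confounding partial and adjustable, at a loss of precision.

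**3. Illustration of size.** Inputs from the Protocol are 25 per group, the t-test and p<0.05. Assumptions are a pooled two-group test, two-sided testing, equal SDs, and the size of the shift, which the documents do not give.

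- Critical observed difference, 48 df: 2.0106 × √(2/25) = 0.569 SD, whatever its origin.
- Rejection probability: P(|T| > 2.0106), with T noncentral t on 48 df and noncentrality d × √(25/2) = 3.536 d.

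| Assumed handling shift, no disease effect (SD) | Probability of p<0.05 |
|---|---|
| 0 | 5% |
| 0.3 | 18% |
| 0.5 | 41% |
| 0.8 | 79% |

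- Masking: 80% power at 25 versus 25 requires a true difference of 0.809 SD. An opposing shift of 0.3 SD leaves 0.509 SD and power 42%; one of 0.5 SD leaves 0.309 SD and power 19%.

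With no handling shift there is no bias, even if every control is purchased.

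**The case against.** **No handling difference is shown.** The Protocol nowhere says that vendor urine is treated differently, and the sentence on aliquoting and -80 °C storage is not expressly limited to Fabry samples. This stands. A reader might infer that the control comparison is biased; the documents do not support that. They support only that the design could neither detect nor remove such a bias. Even if the storage sentence covers vendor urine on receipt, it says nothing about what happened before.

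**The contrast is not a stated aim.** The primary objective and Aims 2 to 4 are framed within Fabry patients. Aim 1 can be answered by comparing patients with and without nephropathy, and the sentence on detecting kidney involvement also reads most naturally as a within-Fabry question. This stands too. A reader might infer that the main objective is compromised; it is not. A Fabry-versus-control comparison is implied by 25 matched controls and is not written out.

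**The figures are generic.** They hold for any 25 versus 25 t-test under the same shift, and the Protocol does not specify a pooled test of that form. Agreed; they do not measure this trial's problem.

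**Controls are well characterised.** A reader might take age and gender matching to be the only comparability stated. That is wrong: health, age range, absence of kidney disease and the control column of Tables 3 and 4 are also given. None of these concerns the specimen, so the confounding remains.

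**Details belong elsewhere.** Vendor specifications often sit in a laboratory manual, and assay layout is not something this text gets wrong. That is fair for layout, which is not part of this point. It does not answer the conflict between the two sections. Nor can a laboratory manual or analysis plan undo complete confounding once the samples have been obtained.

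**The study is labelled descriptive and observational.** The label does not help with attribution: significance tests are still planned, and a descriptive difference is equally confounded.

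**Conclusion.** The conflict between Study population and RECRUITMENT is plain on the text and should be resolved. Purchasing all 25 controls is allowed by both sections and is the only arrangement that Study population describes. In that case disease status and sample source coincide, and a Fabry-versus-control difference in the planned tests could not be attributed to disease rather than to collection or pre-receipt handling. That conclusion follows from the design and needs no assumption about effect size.

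The harm is conditional. It requires that the controls are all purchased, or mostly purchased with no adjustment for source, and that a handling shift exists; the documents give neither its presence nor its size. It is confined to comparisons with controls. Comparisons of naïve with treated patients, and by degree of kidney involvement, all use centre-collected urine and are unaffected. This is a correction that should be made, not a flaw that invalidates the study.

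**What to change.** Before control samples are obtained, state one and the same control source under Study population and RECRUITMENT.

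- **If purchased:** require from the vendor each donor's age and sex, so that the stated matching can be done, and collection, aliquoting and -80 °C storage that match those of the Fabry samples. State in the Protocol that differences from purchased controls are not attributable to disease alone.
- **If recruited in the clinic:** apply the same sample procedure as for the Fabry samples.

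The cost is wording in two sections and, for purchased urine, a vendor specification; whether a vendor can meet it is not known from the documents. Sample size, visits and aims do not change. The downside is a weaker stated conclusion for the control comparison. With all controls purchased, matched handling reduces the confounding but does not remove it, which is why the limit on interpretation is needed as well.

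### The Fabry cohort counts reach 25 only if the naïve patients form a separate group, yet the text lets them sit in other cohorts, so kidney status can be heavily confounded with ERT

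*Protocol*

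**What the plan says.** Under Subject Selection, Number of Subjects, the 50 subjects "include 25 healthy individuals and 25 patients with Fabry disease". Study population then gives "FD patients n=25 (5 without clinical evidence of nephropathy and 15 patients with clinical evidence of nephropathy", followed by 5 naïve patients. The small table under the cohort list repeats 25, 5, 15 and 5.

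The cohort list adds detail:

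- Cohort 1 (n=5) is "FD subjects without clinical evidence of nephropathy (normal eGFR and no microalbuminuria"), and its members may be naïve or treated.
- Cohort 2 (n=15) has three subcohorts: "FD subjects on ERT with CKD stage 1 (estimation n=5"), "FD subjects on ERT with CKD stage 2 (estimation n=5") and "FD subjects on ERT with CKD type 3 a or b (estimation n=5"). All three are on ERT.
- Cohort 3 is the naïve group (n=5). Of it the Protocol says "Can we be included in Cohort group 1 or 2", and then "Additional analysis will be stratified" by naïve versus ERT.

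Under Objective and Specific Aims, the primary objective looks for urinary markers of kidney involvement in naïve patients and compares them with ERT patients to judge what ERT does. Aim 2 asks about kidney involvement within naïve patients. Study type calls the work descriptive and observational. Data management names ANOVA and Student's t-test at p < 0.05, without saying which serves the naïve-versus-ERT contrast.

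**The concern.** Every Fabry patient either has or lacks clinical evidence of nephropathy, and is either naïve or on ERT. The cohort list mixes these two classifications: two rows describe kidney status and the third describes treatment. The reader cannot tell how many distinct patients are naïve, or how many patients in all have nephropathy.

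This matters because the Protocol's own rationale ties nephropathy to activation of the inflammatory pathways being measured. If the naïve patients mostly lack nephropathy and the ERT patients mostly have it, a marker that only tracks kidney damage will look like a difference due to ERT. An analysis plan can adjust for kidney status, but it cannot settle which patients the cohorts were meant to contain. That is fixed here.

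**Working it through.** **1. Reproduce the stated total.** The inputs are the cohort sizes in Study population.

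- Cohorts separate: 5 + 15 + 5 = 25, which matches the stated total.
- Cohort 3 wholly inside cohorts 1 and 2: 5 + 15 = 20, which is 5 short.
- Subcohorts of cohort 2: 5 + 5 + 5 = 15. These are all the places in cohort 2, and all are on ERT.

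The total therefore points to separate recruitment, possibly with the naïve patients regrouped by kidney status for analysis. The sentence on cohort 3 does not say so.

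**2. Nephropathy margins with 25 patients.** Let a be the number of cohort 3 patients with nephropathy (0 to 5) and c the number of cohort 1 patients who are naïve (0 to 5). Keep the 15 ERT patients with nephropathy.

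| | With nephropathy | Without | Total |
|---|---|---|---|
| Naïve | a | 5 − a + c | 5 + c |
| ERT | 15 | 5 − c | 20 − c |
| All | 15 + a | 10 − a | 25 |

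The possible margins are 15/10, 16/9, 17/8, 18/7, 19/6 and 20/5. None is 15/5. The Protocol fixes neither a nor c.

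**3. Bias of an unadjusted contrast.** Assume no ERT effect, a within-cell SD of 1, and a marker shift d due to nephropathy. The Protocol gives no SD or effect size, so d = 0.5, 1 and 1.5 SD are assumptions. The bias is d × (share with nephropathy on ERT − share with nephropathy among naïve).

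- a = 0, c = 0 (0/5 vs 15/20): d × (0.75 − 0) = 0.375, 0.75 and 1.125 SD.
- a = 3, c = 0 (3/5 vs 15/20): d × (0.75 − 0.60) = 0.15 SD at d = 1.
- a = 0, c = 5 (0/10 vs 15/15): d × (1 − 0) = 0.5, 1 and 1.5 SD.

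**4. False rejection by an unadjusted two-sided pooled t-test at 0.05** (400,000 simulated runs per case).

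| Naïve vs ERT with nephropathy | d = 0.5 | d = 1 | d = 1.5 |
|---|---|---|---|
| 0/5 vs 15/20 | 0.103 | 0.251 | 0.447 |
| 3/5 vs 15/20 | 0.047 | 0.039 | 0.029 |

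At 0/10 vs 15/15 each group is uniform in kidney status. False rejection then equals the power of the t-test against d, which is 0.65 at d = 1.

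**5. With adjustment for nephropathy (marker on ERT and nephropathy).**

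- 0/5 vs 15/20: rejection is 0.051. Only the patients without nephropathy inform the contrast, 5 naïve against 5 on ERT, so SE = √(1/5 + 1/5) = 0.632 SD.
- 3/5 vs 15/20: rejection is 0.050. The stratum variances are 1/3 + 1/15 = 0.400 and 1/2 + 1/5 = 0.700, so SE = 1/√(1/0.400 + 1/0.700) = 0.505 SD.
- 0/10 vs 15/15: the nephropathy column equals the ERT column. The design has rank 2 for 3 parameters, and the adjusted contrast cannot be estimated.

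**The case against.** The best reply is that the total of 25 is stated several times and 50 subjects depends on it, so the separate reading is the natural one. With 25 patients, exactly 5 of them naïve, the ERT group still contains 5 patients without nephropathy. Every allocation then leaves naïve patients with ERT counterparts of the same kidney status. This stands. A reader might infer that the Protocol offers no overlap in kidney status at all, and the documents do not support that. Overlap fails at 25 patients only if cohort 1 also turns out to be all naïve, which the wording permits but does not force.

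A reader might also take 0/5 naïve versus 15/15 ERT as the expected case. That needs 20 distinct patients and conflicts with the stated total, so no figure here rests on it.

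A third tempting reading is that the primary objective and Aim 2 both require naïve patients with and without nephropathy. That goes too far. Study design and plan also grades kidney involvement by eGFR and UPCR. Subcohort 2a (GFR above 90 in Table 3) overlaps the normal eGFR of cohort 1, so adjustment for continuous eGFR could be estimated even at 0/10 vs 15/15. Among patients with normal eGFR, however, treatment would then still be tied to microalbuminuria.

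Finally, the false-rejection rates use assumed shifts and an unadjusted test that the Protocol names but does not assign to this contrast, and the subcohort sizes are only estimates. That is correct, and the rates are illustrations. The count conflict does not depend on them.

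**Conclusion.** The point holds as an unresolved conflict in the cohort definitions with a consequence for the primary objective. The with and without nephropathy rows account for 20 of 25 patients. The kidney status of the naïve patients is not assigned, and it is not stated whether naïve members of cohort 1 add to the 5 in cohort 3.

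The size of the consequence depends on the split that is left open. An unadjusted comparison could be nearly harmless (about 4% false rejection at 3/5 vs 15/20 and a 1 SD shift) or seriously misleading (about 25% at 0/5 vs 15/20). These figures assume no ERT effect, equal within-cell SD and a two-sided test. Adjustment largely answers the problem unless cohort 1 is also all naïve. This should be fixed, but it does not invalidate the study.

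**What to change.** Reconcile Study population and its table:

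1. Classify each of the 25 unique Fabry patients once in a treatment (naïve/ERT) by nephropathy (yes/no) table whose cells sum to 25.
2. State whether cohort 3 is a separate group or a cross-classification of cohorts 1 and 2, and whether cohort 1 may contain further naïve patients.
3. Relabel the 15 and 5 to match. If all 20 of those patients are on ERT, for instance, the rows should say so, and the overall margins become 15 + a and 10 − a.
4. Adjust or stratify the naïve-versus-ERT contrast for nephropathy, or for the eGFR and UPCR already measured, instead of relying on an unadjusted t-test or ANOVA. Model detail can sit in the SAP.
5. Report the result as an association adjusted for kidney involvement rather than an effect of ERT, in line with the stated study type.

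A recruitment aim for naïve patients with nephropathy is optional and for the sponsor to decide. It would guard against an empty cell: the chance of 0 in 5 is (1 − p)^5 = 33%, 8% or 1% for assumed shares p of 20%, 40% or 60%. It also reduces recruitment flexibility and gains little at n=5.

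The cost is wording and one table, with no added patients or procedures. The statistical cost is a wider interval if few naïve patients have nephropathy. At 0/5 vs 15/20 and a 1 SD shift, the mean 95% half-width is about 1.30 SD adjusted against 1.10 SD unadjusted. None of this makes Aim 2 precise. A yes/no nephropathy comparison within 5 naïve patients split 3/2 has SE √(1/3 + 1/2) = 0.913 SD and a mean half-width of about 2.7 SD, so it stays descriptive.
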